7.8.9 Immunogenicity

Immunogenicity results will be summarized by treatment group and overall for each scheduled collection visit. Standard descriptive statistics (see [Table 1](#)) will be presented for the observed values. Immunogenicity results will be listed for each subject by treatment group for each scheduled collection visit.

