2.2. Secondary objectives and endpoints

Objective	Endpoint

 To evaluate the proportion of patients achieving FXI inhibition $\geq 50\%$, $\geq 80\%$, and $\geq 90\%$ at trough after the first and second dose (Day 31 and Day 61) at different dose levels of MAA868 	
 Occurrence of achieving $\geq 50\%$, $\geq 80\%$, and $\geq 90\%$ inhibition of FXI ($< 50\%$, $< 20\%$, or $< 10\%$ free FXI) at trough on Day 31 and Day 61 at different dose levels of MAA868

 To evaluate the safety and tolerability following multiple s.c. administration of MAA868 compared to placebo in patients with AF 	
 Occurrence of adverse events (AEs), including serious AEs (SAEs) during the Treatment Period and through EoS

 To evaluate the incidence of major bleeding events, clinically relevant non-major (CRNM) bleeding events and total bleeding with MAA868 relative to placebo during the treatment period 	
 Occurrence of confirmed major bleeding events, CRNM bleeding events and total bleeding events during the treatment period

 To evaluate the immunogenicity of MAA868 compared to placebo. 	
 Screening and confirmation for anti-drug (MAA868) antibodies (ADA)

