8.6. Safety Analysis

The safety evaluation includes the analysis of bleeding events, AEs, major cardiovascular, cerebrovascular, systemic arterial, and venous thromboembolism events, laboratory data, ECG, vital signs, hypersensitivity reactions, injection site reactions, and development of anti-drug antibodies. All safety analysis will be performed using the Safety Set.

Adverse Events

The Investigator’s verbatim term of each AE will be mapped to system organ class (SOC) and preferred term (PT) using the MedDRA dictionary.

Treatment-emergent Adverse Events (TEAEs) will be of primary interest. The TEAEs will be summarized by SOC and PT; a subject will only be counted once per SOC and once per PT within a treatment. If a subject reports more than one AE with the same PT, the AE with the maximum severity will be presented. Subject counts and percentages and event counts will be presented for each treatment and totaled for all treatments for the following summaries:

- All TEAEs
- Serious TEAEs
- All TEAEs by severity
- All TEAEs by relationship to study drug
- TEAEs potentially related to study drug
- TEAEs potentially related to study drug by severity
- TEAEs leading to discontinuation of study drug
- TEAEs leading to withdrawal from the study

Adverse events of special interest (AESI) will be reported for a selection of interested AE terms that are specific to Sponsor's product and program, for which ongoing monitoring and rapid communication by the Investigator to the Sponsor can be appropriate.

The AESIs for this study are defined as follows:

1. TERM 1
2. TERM 2

Similarly, to the TEAE summary, the AESI will be summarized in the following:

1. All AESIs
2. Serious AESIs
3. All AESIs by severity
4. All AESIs by relationship to study drug
5. AESIs leading to discontinuation of study drug
6. AESIs leading to withdrawal from the study

No statistical inference between the treatments will be performed on AEs.

Listings will be presented by subject for all TEAEs, AESIs, as well as for SAEs, TEAEs associated with outcome of death, and TEAEs leading to discontinuation from the study.

Bleeding Events

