8.8. Biomarkers

Coagulation parameters, including free and total FXI, FXI:C, and immunogenicity will be summarized by timepoint and treatment.

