3.2 Secondary Endpoints

Efficacy

- The proportion of subjects achieving $\geq 50\%$, $\geq 80\%$, or $\geq 90\%$ inhibition of FXI ($< 50\%$, $< 20\%$, or $< 10\%$ free FXI) at trough on Day 31 and Day 61 at different dose levels of MAA868.

Safety

- All safety assessment results during the treatment and follow-up periods. Safety endpoints include:
 - Adverse Events (AE)
 - Physical exam
 - Laboratory parameters
 - Vital Signs
 - Electrocardiogram (ECG)
 - Hypersensitivity reactions
 - Injection site reactions
- Occurrence of confirmed major bleeding events, clinically relevant non-major (CRNM) bleeding events, and total bleeding events during the treatment period.
- Identification of anti-drug (MAA868) antibodies using a ligand-binding assay.

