7.1 General Principles

All data processing, summarization and analyses will be performed using Covance's SAS Environment / Version 9.3 (or later) of the SAS® statistical software package.

The following principles will be applied to all TFLs unless otherwise stated:

Table 1: General Principles for the Presentation of Results

Principle	Value
Significant tests and confidence intervals	No significance tests will be conducted for the purpose of this analysis. For the primary efficacy endpoint, a 2-sided 90% confidence interval for the responder rate (%) at trough on Day 91 will be presented by treatment group for MAA868 arms only. For the secondary endpoint, a 2-sided 90% confidence interval for the responder rate (%) at trough on Day 31 and Day 61 will be presented by treatment group for MAA868 arms only.
Treatment group labels and order presented	MAA868 120 mg MAA868 180 mg MAA868 XXX mg (TBD for optional third cohort) Placebo (where applicable) All Subjects (where applicable)
Study phase labels and order presented	Study phase is not relevant to the analysis.
Visit labels and order presented	Listings will present data collected at all visits in the following order:

CONFIDENTIAL

Page 15 of 28

Statistical Analysis Plan

Sponsor Name: Anthos
Sponsor Protocol ID: ANT-004

Covance Study ID: 000000189471

Principle	Value
	
Screening (Visit 1)
 
Visits 2 - 10
 
TD Visit
 
EoS Visit
 
Unscheduled visits will be included in chronological order.
 
Tables will only present visits that correspond to the specified analysis.

Tables	
For endpoints related to inhibition of FXI the data will be tabulated for each trough visit by treatment group.
 
For endpoints related to the occurrence of major bleeding, cardiovascular, cerebrovascular, systemic arterial, and venous thromboembolic events, the data will be tabulated by treatment group.
 
For endpoints related to assessments performed at the study site visits, the data will be tabulated by each treatment group for all applicable scheduled visits.

Listings	
All data collected, as well as derived data used in the analyses, will be presented in listings by population/set, treatment group, and visit (where applicable), unless otherwise specified.

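### The planned ADA table gives per-visit prevalence, not the incidence of antibody development by arm, so the immunogenicity objective versus placebo is only partly addressed

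*SAP*

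**What the plan says.** Immunogenicity is a secondary objective in both documents. Protocol 2.2 words it as "To evaluate the immunogenicity of MAA868 compared to placebo" and gives the endpoint as "Screening and confirmation for anti-drug (MAA868) antibodies (ADA". SAP 3.2 gives the endpoint as "Identification of anti-drug (MAA868) antibodies using a ligand-binding assay". Neither states a variable at subject level.

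On analysis, Protocol 8.6 includes among the safety evaluations "hypersensitivity reactions, injection site reactions, and development of anti-drug antibodies". Protocol 8.8 then says only that "Coagulation parameters, including free and total FXI, FXI:C, and immunogenicity will be summarized by timepoint and treatment". SAP 7.8.9 follows 8.8: "Immunogenicity results will be summarized by treatment group and overall for each scheduled collection visit". Its descriptive statistics "will be presented for the observed values. Immunogenicity results will be listed for each subject by treatment group for each scheduled collection visit".

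Three other provisions bear on the point:

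- Table 1 in SAP 7.1 names "Placebo (where applicable") among the presented groups, and SAP 7.8 presents safety output by actual treatment on the safety set.
- Table 1 also sets the default percentage denominator to everyone in the analysis set, unless the table shells say otherwise.
- Protocol Appendix 4 (Table 9) schedules ADA at Day 1 pre-dose, then at Days 31, 61, 71, 91, 121 and end of study. No ADA sample is scheduled at the treatment discontinuation visit.

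**The concern.** Protocol 8.6 speaks of the development of antibodies. That is a change within a subject: not positive before dosing, positive afterwards. A table of observed results by visit does not measure this, for two reasons.

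First, a subject already positive on Day 1 who stays positive is counted in every post-dose row, although the drug induced nothing. Second, a subject who is positive once appears in a single row, and the rows cannot be added up because the table does not show whether the same people are positive at different visits. Per-visit prevalence can therefore overstate drug-induced ADA through pre-existing reactivity, or understate it through transient responses.

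The neighbouring SAP sections treat their events differently. Bleeding (7.8.8) and cardiovascular and thromboembolic events (7.8.10) are restricted to treatment-emergent events, and a subject is counted once per category. The treatment-emergent definition in 7.8.2 is written for adverse events and is not extended to ADA.

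At stake is a modest but real item of evidence. Protocol 1.2 says the study will help select a dose for phase 3, and the drug is a repeatedly dosed antibody.

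**Working it through.** **The plan's own figure.** The documents state no number for ADA. The only sample-size figure is the exact 90% interval for 11/12 in SAP 2.3, 0.661 to 0.996. The two-sided 90% Clopper-Pearson formula gives 0.6613 to 0.9957, so it reproduces. The same method is used for the intervals below.

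**Inputs.**
- Subjects per active dose: 12, with 4 on placebo per cohort (Protocol 5.3).
- ADA visits: one baseline (Day 1 pre-dose) and six post-dose (Protocol Table 9).
- ADA counts: assumed, since the documents give no expected rate.

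**What a per-visit table can determine.** Let x_v be the number positive at post-dose visit v, and K the number of distinct subjects ever positive after dosing. The table fixes only the bounds

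max(x_v) ≤ K ≤ min(n, Σ x_v).

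**Illustration 1: same rows, different incidence.** Take n = 12 and x_v = 1 at each of six visits.
- Lower bound: max = 1, so 1/12 = 8.3% (exact 90% CI 0.4% to 33.9%). One subject is positive throughout.
- Upper bound: Σ = 6, so 6/12 = 50.0% (24.5% to 75.5%). Six subjects are positive once each.

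Every row reads 1/12 in both cases.

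**Illustration 2: transient responses.** Three of 12 subjects are each positive at a different visit. The highest row is 1/12 = 8.3%; the incidence is 3/12 = 25%.

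**Illustration 3: adding the Day 1 row.** Keep the rows of illustration 1 and let Day 1 also read 1/12.
- If the same subject is positive throughout, nobody is newly positive: 0/12 (0/11 among the baseline-negatives).
- If the Day 1 subject becomes negative and six others are positive once each, 6/12 = 50% are newly positive (6/11 = 54.5% among the baseline-negatives).

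The table is flat at 1/12 from Day 1 to end of study in both cases. Seeing baseline prevalence beside post-dose prevalence therefore does not recover incidence, because the row totals do not link subjects.

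**Precision after the fix.** For 0/12 the two-sided 90% upper limit is 1 − 0.05^(1/12) = 22.1%. For 0/8, placebo pooled over two cohorts (assumed), it is 1 − 0.05^(1/8) = 31.2%.

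**The case against.** The strongest reply is that the plan holds more than the table's wording suggests, and much of that reply stands.

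- *Day 1 is used.* A reader might infer that the baseline sample is ignored, or that pre-existing and post-dose ADA are pooled. The documents do not support this. Day 1 pre-dose is a scheduled collection visit, so it has its own row by arm. What is missing is the within-subject link, and the ambiguity is confined to the post-dose rows.
- *The listing keeps the information.* With 12 active and 4 placebo subjects per cohort and seven ADA visits, baseline status and transient positives can be read off by hand. This is true, but the rule for calling a subject treatment-emergent would then be chosen with results in view. Protocol 5.4 lets the study statistician and programmers hold treatment codes from the start, which is a further reason to fix the rule in advance.
- *Placebo is shown.* A reader might infer that the comparison with placebo is not made at all. That goes too far. The SAP plans no significance tests, and side-by-side prevalence is a descriptive comparison. It is a comparison of prevalence, with the same ambiguity in each arm.
- *The SAP follows Protocol 8.8.* This is correct: 7.8.9 does not depart from the protocol. The gap between development in Protocol 8.6 and the planned summary is present in both documents.
- *The table shells are not in the documents* and could define ADA categories. This cannot be excluded.

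**Conclusion.** The concern holds in a limited form. No treatment-emergent ADA definition and no subject-level count appear in either document. The planned table gives prevalence at each visit and does not determine the incidence of ADA development by arm. The secondary objective versus placebo is partly addressed: a descriptive comparison of per-visit prevalence is available, and a comparison of incidence is not pre-specified. The documents do not support saying that the objective goes unanswered.

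The possible size is wide. Identical post-dose rows of 1/12 fit 8.3% to 50%. These counts are assumptions chosen to show the ambiguity and are not a forecast. If no subject is ever ADA-positive, the per-visit table and an incidence table agree and nothing is lost. The conclusion also assumes that the unseen shells add no subject-level ADA row.

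This is a low-severity point. It touches a descriptive secondary endpoint and leaves the primary analysis unaffected.

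**What to change.** Add to SAP 7.8.9:

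- **Definition.** Treatment-emergent ADA means negative at Day 1 pre-dose and confirmed positive at any post-dose sample through end of study. Using confirmed results also closes the difference between the protocol endpoint, which names confirmation, and the SAP endpoint, which does not.
- **Summary.** Number and percentage of subjects with treatment-emergent ADA, each subject counted once, by dose group and placebo.
- **Denominator.** Subjects with a baseline and at least one post-dose ADA result, stated in the table. The SAP default would keep subjects with no post-dose sample in the denominator, and an early discontinuer may have none because the discontinuation visit takes no ADA sample.
- **Baseline-positive subjects.** Show them in a separate row. A boosted category can be added if titres are measured, which the documents do not say.
- **Per-visit table and listing.** Keep both as supportive output.

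An exact confidence interval and a pooled MAA868 column are optional. Table 1 of the SAP plans intervals only for the efficacy responder rates, and a pooled column is not among its listed groups.

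The cost is a few lines of SAP text and one table. No new sample, visit or subject is needed. The drawback is that the added percentages will be imprecise at 12 per dose: no positives among 12 still leaves an upper limit of 22.1%.

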7.8.10 Cardiovascular, cerebrovascular, systemic arterial, and VTEs

Subject counts and percentages and event counts for the number of treatment-emergent adjudicated cardiovascular, cerebrovascular, systemic arterial, and venous thromboembolic events will be summarized by treatment group and overall. The definition of treatment-emergent can be found in [section 7.7.2](#). If a subject has more than one event in each above category, the subject will be counted only once in the tabulation. All adjudicated events of these type will be listed.

7.9 Pharmacokinetic/Pharmacodynamic Analysis

Individual MAA868 plasma concentrations and PD parameters are evaluated for the PK/PD set and will be summarized by treatment group for each scheduled collection visit/timepoint. PK parameters (listed in [section 4](#)) are evaluated for the PK/PD set and will be summarized by treatment group for the MAA868 arms only. Standard descriptive statistics (see [Table 1](#)) will be presented for the observed values. Individual MAA868 plasma concentrations and all PK parameters will be listed for each subject by treatment group.

Concentrations below the LLOQ will be treated as zero in summary statistics and for PK parameter calculations. A geometric mean will not be reported if the dataset includes zero values.

7.10 Interim Analysis

After approximately 10 of the subjects in cohort 1 have received their second dose of study drug and have been followed for at least an additional 14 days, the safety and tolerability data (AEs, laboratory assessments, vital signs and ECGs) will be evaluated by the Sponsor's Medical Monitor and Covance Lead Project Physician. The decision to proceed to cohort 2 will be made only after:

- It is confirmed that the cohort 1 dose was safe and tolerated
- At least half of the subjects in cohort 1 have been randomized

If notable AEs or safety concerns are found in cohort 1, the study may be terminated.

Likewise, after approximately 10 of the subjects in cohort 2 have received their second dose of study drug and have been followed for at least an additional 14 days, safety, tolerability, and other analyses will be evaluated.

8. Changes in Planned Analysis

There are no changes from planned analyses in the protocol.

9. Data Issues

There are no data issues to report.

10. References

- 1 ICH. *ICH E3 Guideline: Structure and Content of Clinical Study Reports Questions & Answers*, 2012.
- 2 SAS Institute. *SAS/STAT Software*: Cary, NC: SAS Institute; 2003.

Statistical Analysis Plan

Sponsor Name: Anthos
Sponsor Protocol ID: ANT-004

Covance Study ID: 000000189471

11. Appendices

Appendix 1: Document History

Document Version, Status, Date	Summary/Reason for Changes
Version 1, Final, 18 March 2021	SAP draft final review comments

CONFIDENTIAL

Page 28 of 28

Document Date: 18-MAR-2021

ST-AD-008 version 05
